7.3 LOST TO FOLLOW-UP

A participant will be considered lost to follow-up if study staff are unable to contact the participant or care partner after many attempts by phone, email and/or mail. This is unlikely to occur given the relatively short time period of the intervention and the regular contact that most participants and care partners will receive as part of the intervention. If study visits are cancelled multiple times, the study coordinator will counsel the participant and study partner on the importance of maintaining the assigned visit scheduled and ascertain if the participant wishes to and/or should continue in the study. Before a participant is deemed lost to follow-up, the investigator or designee will make every effort to regain contact with the participant and care partner; this will include multiple telephone calls, emails, and/or mailed letter to the participant and care partner. These contact attempts will be documented in the study tracking program with a copy saved in the participant's study file. If the participant continues to be unreachable, he or she will be considered to have withdrawn from the study with a primary reason of lost to follow-up.

8 STUDY ASSESSMENTS AND PROCEDURES

8.1 ENDPOINT AND OTHER NON-SAFETY ASSESSMENTS

Screening

Telephone screening will be conducted to determine eligibility. The study coordinator will first confirm that both the participant and the care partner are interested in participating in the study. After obtaining permission from the participant to ask the care partner questions about the participant's health and every day activities, the care partner will then be asked questions about the functional abilities and health conditions of the potential participant to determine eligibility (See Oral Health Study Phone Screening Report Form). Preliminary eligibility will be determined by the study coordinator at the end of the call. The PI or designee at each site will then review the responses to the health conditions and determine final eligibility. The screening interview should occur within 42 days of enrollment.

Home Visits

The care partner and participant will complete the questionnaires in separate rooms from one another.

Participant Questionnaire:

- Sociodemographics (Baseline) for the study participant including date of birth, gender, years of education completed, race/ethnicity, marital status
- Oral Health Knowledge Scale: Our team has developed a 12-item oral health knowledge scale to assess the knowledge of oral self-care such as frequency and technique of brushing and flossing, duration of brushing, and tongue cleaning that are consistent with general recommendation by dental professionals.³⁷ Oral hygiene behavior (investigator developed) asks about participants' frequency of toothbrushing, flossing, and mouth rinse. The response categories will be coded as 1= Twice a day or more, 2=once a day, 3= Several times a week, 4= Once or less than once a week, 5=Hardly ever, and 6= Never. Geriatric Oral Health Assessment Index³⁸ asks 13 questions about self-perceived oral health. The response categories of each item range from 1=always, 2=sometimes, and 3=never. Xerostomia Inventory³⁹ asks 11 questions about the signs and severity of xerostomia⁸. The responses of each question range from 1=never, to 5=very often. PHQ-8⁴⁰ is an 8-item screen for depression that is administered to the participant.

Care Partner Questionnaire:

- Sociodemographics (Baseline) for the care partner including date of birth, gender, years of education completed, race/ethnicity, marital status, and medical and dental insurance for care partner and for the participant
- Oral Health Knowledge Scale: Our team has developed a 12-item oral health knowledge scale to assess the knowledge of oral self-care such as frequency and technique of brushing and flossing, duration of brushing, and tongue cleaning that are consistent with general recommendation by dental professionals.³⁷
Oral Care Self-Efficacy:⁴¹ Oral care self-efficacy is measured using a slightly modified version of the Geriatric Self-Efficacy Scale for Oral Health measure containing 6 items that assess oral hygiene behaviors.

- Adaptive Leadership Self-Efficacy: The investigators adapted the Caregiver *Confidence in Contributing to Self-Care* to measure ^{42,43}the care partners' confidence in facilitating the participant to perform oral self-care. The measure was originally developed for caregiving in heart failure and has been shown to be reliable and valid in samples of heart failure caregivers. We adapted this 5-item scale (4-point scale) for this study to address care partner confidence in their ability to foster oral self-care in individuals with mild dementia.
- Adaptive Leadership Behaviors-Cueing: The investigators adapted the Caregiver Contribution to Self-Care Management scale to measure use of adaptive leadership cueing strategies by the care partner to facilitate the participant in performing oral self-care. Originally the scale was developed for caregiving in heart failure and has been shown to be reliable and valid in samples of heart failure caregivers.⁴³ We revised the original scale to include 5 items that measure use of verbal, visual, or touch cueing strategies. Each is measured using a 4-point Likert scale (never or rarely, sometimes, frequently, always or daily).
- Adaptive Leadership Behaviors-FOCUSED communication: The investigators adapted the Caregiver Contribution to Self-Care Management scale to measure use of adaptive leadership tailored communication strategies by the care partner to facilitate the participant in performing oral self-care. Originally the scale was developed for caregiving in heart failure and has been shown to be reliable and valid in samples of heart failure caregivers.⁴³ We revised the original scale to 9 items that measure use of FOCUS communication strategies.
- Participant oral hygiene behavior (investigator developed) asks about the participants' frequency of toothbrushing and flossing. The response categories will be coded as 1= Twice a day or more, 2=once a day, 3= Several times a week, 4= Once or less than once a week, 5=Hardly ever, and 6= Never. This measure also includes the frequency of reminders that the care partner provides. The response categories include 1=Very often, 2=Sometimes, 3=Occasionally, and 4= Not at all
- Own oral hygiene behavior (investigator developed) asks about care partners' frequency of toothbrushing, flossing, and mouth rinse. The response categories will be coded as 1= Twice a day or more, 2=once a day, 3= Several times a week, 4= Once or less than once a week, 5=Hardly ever, and 6= Never.

Study coordinator collects data from log and a smart toothbrush

- Oral hygiene behavior data collected from log for Treatment Group 2: Duration of toothbrushing and frequency of toothbrush. Duration of brushing will be measured as a continuous variable; frequency will be coded as an ordinal variable, 1-3.
- Oral hygiene behavior data from a smart toothbrush for Treatment Group 1 and 2: Duration of toothbrushing and frequency of toothbrushing. Duration of brushing will be measured as a continuous variable; frequency will be measured as a continuous variable..

After both sets of questionnaires are completed, the dental hygienist will perform a complete oral health evaluation on the participant:

- Determination of missing teeth (Number of missing teeth coded as a continuous variable.)
- Plaque Index⁴⁴ using UNC Modified Green and Vermillion Oral Hygiene Index (1960) Plaque will be measured as 0= No plaque, 1=Plaque covers < 1/3 tooth, 2=Plaque covers >=1/3 but < 2/3 tooth, and 3=Plaque covers >=2/3 tooth.

- Gingival Index⁴⁵ using UNC Modified Loe and Silness Gingival Index. Gingival inflammation is classified as 0 = Normal gingiva, 1 = Mild inflammation, no bleeding on probing, 2 = Moderate inflammation, bleeding on probing, 3 = Severe inflammation, tendency to spontaneous bleeding.
- Score of overall oral health using the OHAT⁴⁶ assessment sheet. A modification of the Brief Oral Health Status Examination that was developed specifically for older adults with cognitive impairment. OHAT measures eight categories: lips, tongue, gums and tissues, saliva, natural teeth, dentures, oral cleanliness and dental pain. Each category is coded as 0 (unhealthy), 1 (changes), and 2 (healthy). The data collected during the oral evaluation will be manually transcribed by a dental recorder and will be audio recorded. At this point, the dental hygienist will complete the General Examination Recommendation Sheet which will inform the participant if there are any urgent dental problems present. If urgent problems are present, the participant and care partner will be informed and referred to a dentist for treatment.
- Oral hygiene skills: The hygienist measures the appropriateness, quality, and duration of toothbrushing. It is coded as continuous variable, ranging from 3-9.
- Alzheimer's Disease Cooperative Studies Activities of Daily Living Instrument (ADCS ADL). The ADCS ADL is administered to the care partner to assess the participant's functional ability during the previous 4 weeks to complete 27 daily activities. If the activity was attempted, then the care partner was asked if the participant completed the activity 'independently', 'with supervision', or 'with physical help'. Each activity will be coded as 0=need some assistance, 1=independent without any help. A summary score ranges from 0-27. This instrument will be administered at baseline to better characterize the level of cognitive and functional impairment of the participants.
- Current medications - All medications taken during the previous two weeks will be reviewed and recorded by the dental hygienist, collected by medicine chest inventory by study staff. This screening is to confirm eligibility of study participant.
- Montreal Cognitive Assessment (MoCA)⁴⁷ is a brief cognitive assessment measure with a maximum of 30 points. It has been widely used and validated in many populations, the score ranges from 0-30. We will use the actual score to measure participant's cognitive function.

In a post-intervention interview at the last visit, all participants and care partners will be asked about their experience in the study using the guide developed in the pilot study.

8.2 SAFETY ASSESSMENTS

ASSESSMENT OF SAFETY

During the oral evaluation conducted at each study visit, the hygienist will assess whether the participant's mouth has signs of inappropriate oral hygiene behaviors that are damaging the teeth or gums.

CLINICAL SITE MONITORING

Internal Monitoring: The research team will monitor safety issues on an ongoing basis. Adverse event data reports will be available to the research team on a monthly basis. All deaths and any serious

adverse events will be reported according to procedures stated in this protocol regardless of relation to the study.

Safety monitoring plan

We will document, track and report safety issues as noted elsewhere in the protocol.

8.3 ADVERSE EVENTS AND SERIOUS ADVERSE EVENTS

8.3.1 DEFINITION OF ADVERSE EVENTS

An adverse event (AE) is any untoward medical occurrence which does not necessarily have a causal relationship with this study intervention. There are no safety implications from participation in the study. AEs may also include the following: Intervention complications that occurs as a result of a protocol-mandated procedure (e.g., brushing teeth with electrical toothbrush) during or after screening.

8.3.2 DEFINITION OF SERIOUS ADVERSE EVENTS

A serious adverse event (SAE) is one that meets one or more of the following criteria:

- Results in death
- Is life-threatening (places the participant at immediate risk of death from the event as it occurred)
- Results in inpatient hospitalization or prolongation of existing hospitalization
- Results in a persistent or significant disability or incapacity
 - An important medical event that may not result in death, be life threatening, or require hospitalization may be considered an SAE when, based upon appropriate medical judgment, the event may jeopardize the participant and may require medical or surgical intervention to prevent one of the outcomes listed in this definition.

8.3.3 CLASSIFICATION OF AN ADVERSE EVENT

8.3.3.1 SEVERITY OF EVENT

The following guidelines will be used to describe severity of adverse events.

- **Mild:** Events require minimal or no treatment and do not interfere with the participant's daily activities.
- **Moderate:** Events result in a low level of inconvenience or concern with the therapeutic measures. Moderate events may cause some interference with functioning.

- **Severe:** Events interrupt a participant's usual daily activity and may require systemic drug therapy or other treatment. Severe events are usually potentially life-threatening or incapacitating. Of note, the term "severe" does not necessarily equate to "serious".

8.3.3.2 RELATIONSHIP TO STUDY INTERVENTION/EXPERIMENTAL MANIPULATION

All reported adverse events (AEs) will relate to the study procedures or the intervention as assessed by an appropriately-trained investigator. The degree of certainty about causality will be graded using the categories below.

- **Related:** The AE is known to occur with the study procedures or the intervention, there is a reasonable possibility that the study procedures or the intervention caused the AE, or there is a temporal relationship between the study procedures and the event. Reasonable possibility means that there is evidence to suggest a causal relationship between the study procedures and the AE.
- **Not Related:** There is not a reasonable possibility that the study procedures caused the event, there is no temporal relationship between the study procedures and event onset, or an alternate etiology has been established.

8.3.3.3 EXPECTEDNESS

The principal investigators will be responsible for determining whether an adverse event (AE) is expected or unexpected. An AE will be considered unexpected if the nature, severity, or frequency of the event is not consistent with the risk information previously described for the study procedures. This study is considered to be at minimum risk.

8.3.4 TIME PERIOD AND FREQUENCY FOR EVENT ASSESSMENT AND FOLLOW-UP

All adverse events (AEs) and serious adverse events (SAEs) that are spontaneously reported to study personnel or elicited by them during subject interviews or contacts will be systematically assessed. The coordinator will maintain a tracking log of all AEs and SAEs. For all reportable AEs and all SAEs, details of the event will be collected and recorded in RedCap. Information to be collected includes event description, time of onset, assessment of severity, relationship to study procedures (assessed only by those with the training and authority to make a diagnosis), and time of resolution/stabilization of the event. All reportable AEs and all SAEs will be followed to adequate resolution.

Any medical or psychiatric condition that is present at the time that the participant is screened will be considered as baseline and not reported as an AE. Some participants' health conditions may decline during the study period. If the study participant's condition deteriorates significantly during the study, it will be recoded as an AE.

The principal investigators or research staff will record events with start dates occurring any time after informed consent is obtained until 7 (for non-serious AEs) or 30 days (for SAEs) after the last day of study participation.

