1.3 SCHEDULE OF ACTIVITIES

Treatment Group 1

| Treatment Group 1 | Screening | Time 1 (Home Visit 1) Week 1: (within 42 days of screening) | Time 2 Week 4: (± 7 Days) | Time 3 Week 8: (± 7 Days) | Time 4 (Home Visit 2) Week 12: (± 14 Days) | Time 5 Week 16: (± 7 Days) | Time 6 Week 20: (± 7 Days) | Time 7 (Home Visit 3) Week 24: (± 14 Days) |
|-------------------------------------|-----------|--|---------------------------------|---------------------------------|---|----------------------------------|----------------------------------|---|
| Screen for eligibility | X | | | | | | | |
| Obtain verbal informed consent | X | | | | | | | |
| Schedule Visit 1 | X | | | | | | | |
| Obtain written informed consent | | X | | | | | | |
| Care Partner Questionnaire | | X | | | X | | | X |
| Study Participant Questionnaire | | X | | | X | | | X |
| Oral Health Evaluation | | X | | | X | | | X |
| ADCS-ADL | | X | | | | | | |
| Oral Hygiene Skill Assessment Sheet | | X | | | X | | | X |
| Coaching Module | | | | | | | | |
| Tailored Oral Hygiene Instruction | | | | | | | | |

| Treatment Group 1 | Screening | Time 1 (Home Visit 1) Week 1: (within 42 days of screening) | Time 2 Week 4: (± 7 Days) | Time 3 Week 8: (± 7 Days) | Time 4 (Home Visit 2) Week 12: (± 14 Days) | Time 5 Week 16: (± 7 Days) | Time 6 Week 20: (± 7 Days) | Time 7 (Home Visit 3) Week 24: (± 14 Days) |
|---|-----------|--|---------------------------------|---------------------------------|---|----------------------------------|----------------------------------|---|
| Montreal Cognitive Assessment (MoCA) | | X | | | X | | | X |
| Educational booklet provided | | X | | | | | | |
| Electronic Toothbrush Data Download | | | X | X | X | X | X | X |
| Detailed explanation of education booklet | | | | | | | | X |
| Exit Interview w/participant | | | | | | | | X |
| Exit Interview w/care partner | | | | | | | | X (via phone) |

Treatment Group 2

| Treatment Group 2 | Screening | Time 1 (Home Visit 1) Week 1: (within 42 days) | Time 2 Week 4: (± 7 Days) | Time 3 Week 8: (± 7 Days) | Time 4 (Home Visit 2) Week 12: (± 14 Days) | Time 5 Week 16: (± 7 Days) | Time 6 Week 20: (± 7 Days) | Time 7 (Home Visit 3) Week 24: (± 14 Days) |
|---------------------------------|-----------|---|---------------------------------|---------------------------------|---|----------------------------------|----------------------------------|---|
| Screen for eligibility | X | | | | | | | |

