| Obtain verbal informed consent | X | | | | | | | |
| Schedule Visit 1 | X | | | | | | | |
| Obtain written informed consent | | X | | | | | | |
| Care Partner Questionnaire | | X | | | X | | | X |
| Study Participant Questionnaire | | X | | | X | | | X |
| Oral Health Evaluation | | X | | | | | | |
| ADCS-ADL | | X | | | | | | |

| Treatment Group 2 | Screening | Time 1 (Home Visit 1) Week 1: (within 42 days) | Time 2 Week 4: (± 7 Days) | Time 3 Week 8: (± 7 Days) | Time 4 (Home Visit 2) Week 12: (± 14 Days) | Time 5 Week 16: (± 7 Days) | Time 6 Week 20: (± 7 Days) | Time 7 (Home Visit 3) Week 24: (± 14 Days) |
|---|-----------|---|---------------------------------|---------------------------------|---|----------------------------------|----------------------------------|---|
| Oral Hygiene Skill Assessment Sheet | | X | | | X | | | X |
| Coaching Module | | X | X (via phone) | X (via phone) | X | | | |
| Tailored Oral Hygiene Instruction | | X | | | X | | | |
| Montreal Cognitive Assessment (MoCA) | | X | | | X | | | X |
| Educational booklet provided and reviewed | | X | | | | | | |
| Electronic Toothbrush Data Download | | | X | X | X | X | X | X |

| Treatment Group 2 | Screening | Time 1 (Home Visit 1) Week 1: (within 42 days) | Time 2 Week 4: (± 7 Days) | Time 3 Week 8: (± 7 Days) | Time 4 (Home Visit 2) Week 12: (± 14 Days) | Time 5 Week 16: (± 7 Days) | Time 6 Week 20: (± 7 Days) | Time 7 (Home Visit 3) Week 24: (± 14 Days) |
|--|-----------|--|---------------------------------|---------------------------------|--|----------------------------------|----------------------------------|--|
| Post Intervention Interview—participant | | | | | X | | | |
| Post Intervention Interview-Care partner | | | | | X (via phone) | | | |
| Exit Interview w/participant | | | | | | | | X |
| Exit Interview w/care partner | | | | | | | | X (via phone) |

Control Group

| Control Group | Screening | Time 1 (Home Visit 1) Week 1: (within 42 days) | Time 2 Week 4: (± 7 Days) | Time 3 Week 8: (± 7 Days) | Time 4 (Home Visit 2) Week 12: (± 14 Days) | Time 5 Week 16: (± 7 Days) | Time 6 Week 20: (± 7 Days) | Time 7 (Home Visit 3) Week 24: (± 14 Days) |
|-------------------------------------|-----------|---|---------------------------------|---------------------------------|---|----------------------------------|----------------------------------|---|
| Screen for eligibility | X | | | | | | | |
| Obtain verbal informed consent | X | | | | | | | |

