Informal caregivers play a pivotal role in caring for individuals with mild dementia and thus are an important resource for individuals with mild dementia. Three-fourths of the about 1.5 million individuals with mild dementia¹⁷ in the U.S. receive assistance, reminders, or supervision for daily activities from caregivers such as spouses or adult children.¹⁸ Yet, oral hygiene tasks are often neglected.¹⁹ Structured assistance in the form of caregiver-assisted interventions has proven to be useful in studies of other outcomes involving individuals with mild dementia, such as improved memory performance.²⁰ Including the caregiver as a partner (i.e. care partner) in the intervention has distinct benefits in preventing oral health decline among individuals with mild dementia. To our knowledge, this will be the first intervention incorporating assistance of informal caregivers to improve oral health for individuals with mild dementia^{21,22}. Our rationale is that individuals with mild dementia characteristically have trouble learning complex new tasks or performing multi-step tasks, such as following a recipe or performing complex household chores; yet they retain procedural memory, the ability to remember how to perform simple well-learned everyday tasks. The basic steps and motions involved in toothbrushing use procedural memory.²³ Thus, individuals with mild dementia often can continue to perform routine hygiene tasks to a large extent independently. In this intervention, care partners will learn to create routines and break oral care into discrete steps that will help lead the participant through the procedures of oral self-care.

The third significant aspect of our study is our use of an objective measure of toothbrushing behavior. Most interventions have relied on self-reported information on frequency and duration of toothbrushing. Even cognitively intact adults are susceptible to recall errors.²⁴ Among memory impaired individuals, this issue is even more of a problem. Thus, we will use a smart electronic toothbrush that records time and duration of use, providing a more reliable and valid assessment of behavior than self-report.

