9.4.4 SAFETY ANALYSES

N/A

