10.1.6 SAFETY OVERSIGHT

Safety oversight will be under the direction of a Data and Safety Monitoring Board (DSMB) composed of individuals with the appropriate expertise, including dentistry and behavioral interventions. Members of the DSMB should be independent from the study conduct and free of conflict of interest, or measures should be in place to minimize perceived conflict of interest. The DSMB will meet at least semiannually to assess safety and efficacy data on each arm of the study. The DSMB will operate under the rules of an approved charter that will be written and reviewed at the organizational meeting of the DSMB. At this time, each data element that the DSMB needs to assess will be clearly defined. The DSMB will provide its input to National Institutes of Health, National Institute of Dental and Craniofacial Research.

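### Adverse events are collected at contacts that differ by arm, and no by-arm safety table is planned, so AE counts are open to ascertainment bias and the check for brushing damage has no defined result

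*Combined protocol and SAP*

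**What the plan says.** Section 8.3.4 defines AE capture by route: events "that are spontaneously reported to study personnel or elicited by them during subject interviews or contacts will be systematically assessed". Events starting at any time after consent are recorded. The Schedule of Activities (Section 1.3) has no AE row in any arm.

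Both treatment arms have the row "Electronic Toothbrush Data Download | | | X | X | X | X | X | X", that is, activity at weeks 4, 8, 12, 16, 20 and 24. TG2 also has "Coaching Module | | X | X (via phone) | X (via phone) | X". The control table shows activity after baseline only at weeks 12 and 24. Section 7.3 expects few losses partly because of "the regular contact that most participants and care partners will receive as part of the intervention".

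Section 10.1.6 has the DSMB meet at least twice a year "to assess safety and efficacy data on each arm of the study". Section 8.2 has the hygienist look at each study visit for "signs of inappropriate oral hygiene behaviors that are damaging the teeth or gums". Section 8.3.1 gives electric toothbrushing as an example of a source of complications that may count as AEs. The section headed "9.4.4 SAFETY ANALYSES" contains only N/A.

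**The concern.** When events are picked up at whatever contacts occur, the arm with more contacts tends to show more events, above all minor ones that pass and are forgotten. Here contact frequency is part of what distinguishes the arms. A DSMB comparing AE counts by arm could see an excess under the brush or coaching that reflects only how often somebody asked.

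The hygienist's check is tied to study visits meant to be common to all arms, so unequal contact does not distort it. It is also the observation closest to the harm that the protocol itself names. Yet nothing says how the finding is recorded or that it will be compared between arms. The final report could then lack a by-arm statement on harm while the one by-arm safety view in the protocol is hard to interpret.

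**Working it through.** The plan states no AE rate and no number of AE contacts, so there is no figure to reproduce.

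**1. Scheduled time points after baseline (Section 1.3).**
- Control: weeks 12 and 24 = 2. Its download row is empty.
- TG1: visits at weeks 12 and 24, and a download alone at weeks 4, 8, 16 and 20. That is 2 + 4 = 6 if downloads are conversations, and 2 if they are not.
- TG2: visits at weeks 12 and 24 and coaching calls at weeks 4 and 8 = 4. Downloads alone at weeks 16 and 20 bring this to 6.

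Section 4.1 says that the study coordinator downloads monthly, but not whether in person, by phone or remotely. Ratios to control are 6/2 = 3.0, 4/2 = 2.0 or 2/2 = 1.0. Counting baseline as well, the largest is 7/3 = 2.33.

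**2. What this could do to AE counts.** Assume a constant event rate over 24 weeks, the same enquiry at every contact, and that an event is reported only if it began within *w* weeks before a contact. The share captured is the sum of min(*w*, gap) over the gaps between contacts, divided by 24. Gaps are 12, 12 in control; six of 4 with monthly contact; and 4, 4, 4, 12 for TG2 on calls and visits alone. For *w* = 4: control (4 + 4)/24 = 33%; monthly (6 × 4)/24 = 100%; TG2 calls and visits (4 + 4 + 4 + 4)/24 = 67%.

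| Assumed *w* (weeks) | Control | Monthly contact (TG1, TG2) | Ratio | TG2, calls and visits only | Ratio |
|---|---|---|---|---|---|
| 2 | 17% | 50% | 3.0 | 33% | 2.0 |
| 4 | 33% | 100% | 3.0 | 67% | 2.0 |
| 6 | 50% | 100% | 2.0 | 75% | 1.5 |
| 8 | 67% | 100% | 1.5 | 83% | 1.25 |
| 12 | 100% | 100% | 1.0 | 100% | 1.0 |

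TG1 with remote downloads equals control in every row (ratio 1.0). SAEs, being memorable, belong near the bottom of the table.

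**3. Following the damage check to an output.** Section 8.2 creates the observation. Section 8.1 lists the hygienist's measures and a sheet for urgent dental problems, but no scale or field for this finding. Section 9.4.4 is N/A. SAP Tables 1 and 2 are demographics, Table 3 primary and secondary outcomes, Table 4 mediators, Table 5 knowledge items, and Table 6 knowledge score and cueing. None holds AEs, SAEs or damage. The remaining route is classification as an AE (8.3.1), then the tracking log (8.3.4), then annual reports to the IRB and DSMB (8.3.5).

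**4. Whether the check occurs in TG2.** The TG2 schedule marks the oral health evaluation at Time 1 only. Table 2 in Section 6.1.1 lists the in-home oral exam at baseline, 3 and 6 months. The two must be reconciled, because the damage check is made during that evaluation.

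**The case against.** A reader might infer that contact is three times as frequent in both treatment arms. The documents do not establish this: it requires every download to be a conversation, and otherwise TG1 is level with control. TG2 still has at least 4 contacts against 2.

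A reader might also infer that the DSMB's counts are biased, not merely open to bias. The home visits at weeks 12 and 24 can pick up earlier events in every arm, and with full 12-week recall the distortion disappears. The remark in Section 2.1 that "Among memory impaired individuals, this issue is even more of a problem" concerns self-reported brushing, not medical events. The informant need not be the participant either: eligibility requires a co-resident care partner, who completes a questionnaire at all three home visits. What the DSMB will be shown is left to a charter that is not among the documents.

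Finally, a reader might infer that brushing damage never reaches any result, or that the trial can say nothing on harm. Damage recorded as an AE reaches the log and the annual reports. Gingival inflammation is a primary outcome compared by arm, which covers part of any gum harm, though not abrasion.

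These points remove the stronger readings. They leave the absence of a common enquiry, the unequal schedule and the absence of any planned by-arm safety output. Section 8.3.3.3 regards the study as minimum risk, which argues for a light remedy rather than none.

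**Conclusion.** The concern holds in a limited form. AE ascertainment is opportunistic, and scheduled post-baseline contacts are 2 in control, 4 to 6 in TG2 and 2 to 6 in TG1. By-arm counts of non-serious AEs are open to ascertainment bias, probably toward the treatment arms. Its size cannot be fixed from the documents: none to about threefold, resting on the assumed recall window and on how downloads are made. SAEs should be little affected.

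Separately, and without any assumption, no by-arm table of AEs, SAEs or brushing damage is planned in Section 9 or the SAP, and the damage check has no defined variable. The check is insulated from unequal contact but not from knowledge of assignment, since Section 6.3 says that research staff are not blind.

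**What to change.** 1. At Home Visits 2 and 3 in every arm, ask the care partner one identical scripted AE question covering the whole interval since the previous home visit, including events already reported at monthly contacts. Base the by-arm comparison of non-serious AEs on those answers. Show SAEs, and all AEs from any source, alongside by arm, and record the contact at which each was first reported. Do not restrict the comparison to events first found at home visits: that would drop treatment-arm events reported at weeks 4, 8, 16 or 20 while counting the same events in control, and so reverse the bias. Extra control calls are not needed and could change that group's behaviour.
2. Replace N/A in Section 9.4.4 with a descriptive by-arm table of AEs, SAEs and the hygienist's damage finding (yes/no) at baseline, 3 and 6 months. Add it to the SAP, noting that assessors are unblinded.
3. Reconcile the TG2 schedule with Table 2 on the timing of the oral health evaluation, and state how downloads are made.
4. The SAP reports 60 dyads consented and 54 completed as of 05/08/24, so the question helps only visits still to come. For completed visits, tabulate AEs and SAEs by arm and by contact of first report, and state unequal contact as a limitation.

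The cost is one question at existing visits, one log field and one descriptive table. The damage item needs a recorded yes/no field if none exists, and cannot be tabulated for past visits where it was not recorded.
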